## 4.0 Study Endpoints and Rationale

### 4.1 Primary Study Endpoints

The primary aims of this study focus on characterizing the relationship between changes in pharmacodynamic markers and clinical outcome measures, when inter-subject variability in ATX pharmacokinetics has been minimized (Fig. 3). ATX pharmacodynamics will be measured using plasma DHPG and metabolomic data, pupillometry during attention tasks, and changes in blood pressure and heart rate. Clinical outcomes will be assessed by standardized ADHD measures used in a clinical setting, of which include: NICHQ Vanderbilt Assessment Scale (ADHD symptom rating scale); Strengths and Difficulties Questionnaire; Child Behavior Checklist; the School Intervention Questionnaire; Medication Side Effects; and Clinical Global Impression. Some of these questionnaires will also capture comorbidity information, such as Oppositional Defiant Disorder (ODD). We will also use the Kiddie Schedule for Affective Disorders and Schizophrenia for School-Age Children – Present and Lifetime Version (K-SADS-PL) or K-SADS-COMP (the computerized version of the K-SADS-PL) to diagnose ADHD and commonly associated comorbidities. The K-SADS-PL is a semi-structured interview that is extensively used in clinical psychology research to diagnose an extensive array of psychopathology based on the DSM-5. Given the length of this interview, common research practices are to select only the modules that are expected to be pertinent to the study participant (Black et al., 2012; Kariuki et al., 2018; Caudle et al., 2020). The K-SADS-PL modules selected for this research study are as follows: agoraphobia, separation anxiety disorder, social anxiety disorder/selective mutism, specific phobias, generalized anxiety, obsessive compulsive disorder, and post-traumatic stress disorder. The other research comorbidities or impairments that we will assess for and associated psychometric tests we will use are as follows: impairment in executive function using the Behavior Rating Inventory of Executive Function (BRIEF); anxiety using the Screen for Child Anxiety and Related Disorders (SCARED); intelligence quotient using the Kaufman Brief IQ Test (KBIT); and sluggish cognitive tempo using the Barkley Sluggish Cognitive Tempo Scale (SCT). Pharmacodynamic data will be obtained: baseline (Research Visit 1); when ATX is first initiated in a participant with the first dose (Research Visit 2); when the participant has taken the medication chronically and thus, expected to be at steady-state (Research Visit 3); and at the end of study when the dose has been optimized for the participant (Research Visit 4). Concurrent pharmacokinetic analysis will take place to ensure that ATX plasma and urine exposure variability has been minimized using methods described in a previous ATX pharmacokinetic study conducted at Children's Mercy Hospital (Brown et al., 2016). Additionally, we will measure ATX and metabolites in sweat as surrogate for fraction of drug unbound (Marchei et al., 2012; Marchei et al., 2013). The clinical ADHD questionnaires will be administered at the Intake Visit and at follow-up visits following initiation of atomoxetine treatment (6-weeks, 12-weeks, and

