the opportunity to practice the tasks (3 trials). Measurements will be recorded for 162 trials which for both localization and discrimination tasks. Eye-moment, dilation, and reaction time will be measured during all tasks. Please see **Figures 1 and 2** in the Appendix H of this document. **Figure 1** illustrates an example of a valid and invalid trial for successful completion of the localization task, while **Figure 2** illustrates an example of a valid and invalid trial for successful completion of the discrimination task.(Aston-Jones and Cohen, 2005; Alnaes et al., 2014)

Secondary Study Endpoints:

The secondary aims focus on: exploring baseline patient characteristics that may predispose an individual to have beneficial clinical response from ATX therapy; refinement of the iGO-PK dosing algorithm; exploration of the role of the microbiome in impacting ATX pharmacokinetics and pharmacodynamics; validation of a urinary CYP2D6 biomarker; and exploring ways improve study participant understanding of research procedures. A previous study with an anti-depressant, citalopram, suggests that the ability to respond positively to a medication may be predicted given an understanding of the individuals' composite of signaling molecules, i.e. the global neurotransmitter profile. We are interested in comparing the baseline global neurotransmitter profile between children who do and do not respond. We are also interested in understanding how the neurotransmitter profile changes with chronic ATX use and correlating these changes with clinical benefit of toxicity. To do this, we will evaluate a panel of approximately 30 neurotransmitters (Gupta et al., 2016)(refer to Appendix I for example list) prior to treatment and during treatment with ATX.

Because there is evidence that the gut microbiome can to influence host neurotransmitter concentrations (Petra et al., 2015), we would like to evaluate this as a possible confounder to the global neurotransmitter profile. Given that the oral and gut microbiome landscape correlate well with one another (Zhang et al., 2015) we will also sample saliva to account for factors that could contribute to an individual's neurotransmitter make-up.

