## SHORT TITLE: ATX-PBPK-PD-Clinical Outcomes (U54)

Pharmacokinetic sample (urine)				X	X				X	
Microbiome sample (saliva)		X		X	X				X	
Schedule of Events	Prescreen	Research Visit 1* θ	Intake with Study Physician ψ	Research Visit 2*	Research Visit 3*	6-Week Visit with Study Physician ψ	12-Week Visit with Study Physician ψ	18-Week Visit with Study Physician ψ	Research Visit 4*	2-week Post-Study Check
Sweat patches (sweat)				X	X				X	
Pupillometry during Posner's Cuing Task		X		X	X				X	
Dietary Survey Questionnaire									X	
Kiddie Schedule for Affective Disorders and Schizophrenia (KSADS)		X								
Kaufman Brief IQ Test (KBIT)		X								
Behavior Rating Inventory of Executive Function (BRIEF)		X							X	
Barkley Sluggish Cognitive Tempo Scale (SCT)		X							X	
Screen for Child Anxiety and Related Disorders (SCARED) – parent		X							X	

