Estimation of the pharmacodynamics parameters and generation of statistical analyses will be performed by The Division of Clinical Pharmacology, Toxicology & Therapeutic Innovation at the Children's Mercy Hospital, Kansas City, MO. An indirect model of pharmacodynamic changes, using change in plasma DHPG as a function of systemic plasma ATX concentration will be evaluated using Phoenix NLME (Certara, Princeton, NJ, USA), NONMEM (Icon, Dublin, Ireland), MATLAB (Natick, MA, USA), SAS version 9.4 (SAS, Cary, NC, USA), and R (The R Foundation). Concentration changes in DHPG as a function of change in systemic ATX levels will be fit to an indirect model (Equation A). Pharmacodynamic parameters  $k_{in}$ ,  $k_{out}$ ,  $I_{max}$ , and  $IC_{50}$  will be estimated for each metabolite studied using a nonlinear mixed effects model to take into account variability of pharmacodynamic marker change within the study population. Statistical regression models will be constructed to determine which patient covariates are

predictive of pharmacodynamic response. A maximal effect ( $E_{max}$ ) model describing the relationship between ATX concentration and pharmacodynamic effect will also be assessed in this study (Equations B and C). Models will be compared using statistical tests (Sum of Squares, Loglikelihood, AIC, standard error of estimates, and distribution of residuals). Changes in ATX  $C_{max}$  and  $AUC_{0-\infty}$  will also be plotted against pupillometry and eye-tracking data gathered when testing participants with localization and discrimination tasks. To describe the relationship between attentional orientating as function of ATX exposure, the data will be regressed both linearly and non-linearly and best of fit statistics (Akaike Information Criteria and Bayesian Information Criteria) will be employed to determine the most appropriate model.

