#### Pupillometry Analysis:

Changes in performance during Posner Cuing Task will be measured as a function ATX exposure and  $C_{max}$  concentrations. Pupil size will be measured during two types of activities: localization and discrimination tasks. Pupil size differences during localization tasks report on the individuals' baseline (tonic) release of norepinephrine. This corresponds to endogenous, or volitional attention. Pupil size differences during discrimination tasks is a composite of the individuals' baseline (tonic) and situational (phasic) release of norepinephrine. Currently it is unclear whether tonic, phasic, or both are impaired in individuals with ADHD.

Cardiovascular Marker Analysis:

Changes in heart rate will also be measured as a function ATX exposure and  $C_{max}$  concentrations. One side effect of ATX that is directly related to the pharmacodynamics of the drug is an increased heart rate due to increased concentration of norepinephrine in blood. We would like to understand the extent of this side effect as a function of increased systemic ATX exposure and  $C_{max}$ . By studying these two components, we will be able to distinguish ATX drug action in central and peripheral nervous systems.

Pharmacodynamic Changes Correlated with change in NICHQ Vanderbilt Assessment Scales:

All changes markers of pharmacodynamic action will be correlated with whether a child is classified as a responder or non-responder; and tolerant or intolerant (see Clinical Outcomes below for details). Extent of adherence will be used as a confounding factor in both of these analyses.

Clinical Outcomes:

Determine and document participant response to ATX therapy:

- Responders will be defined as:
  - Participants, who after approximately 18 weeks of continuous treatment with ATX, demonstrate  $\geq 40\%$  reduction of baseline ADHD symptom score;
  - OR the Clinical Global Improvement rating is 1 or 2 (Very Much Improved or Much Improved).
- Non-responders will be defined as:
  - Participants, who after approximately 18 weeks of continuous treatment with ATX, demonstrate  $< 40\%$  reduction of baseline ADHD symptom score, AND the Clinical Global Improvement score  $\geq 3$ .
  - Participants who discontinue ATX prior to the planned end of study (18 weeks) due to perceived lack of efficacy despite dose escalation.

Determine and document participant tolerance of ATX therapy:

- ATX intolerant participants are:

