ATX pharmacodynamic data for each *SLC6A2* activity group will be examined using standard descriptive statistics. Analysis of variance will be used to compare parameters between pre-defined genotype populations followed by application of the appropriate parametric or non-parametric post-hoc test to determine where inter-group differences occur. Linear and non-linear least squares regression analysis will be used to examine the correlation between DHPG fitted parameters and changes in eye-tracking and pupillometry differences in *SLC6A2* genotype groups. Univariate analysis of variance, nonlinear regression and analysis of covariance will be used to evaluate the relationship between demographic variables (alone or in combination) with corresponding pharmacodynamic parameter estimates. All analyses will be performed in SPSS version 11.5 (SPSS, Chicago, IL) with the significance limit set at  $\alpha=0.05$ . A sample size of 120 was deemed reasonable with the volume of patients being referred to the ADHD sub-specialty over a four year period. Powering of statistical tests was done assuming 20% attrition and data simulated for 96 patients. Assuming that 30% of the participants completing the study are categorized as responders, an  $\alpha = 0.05$ , and power = 80%, a mean difference in covariates assessed of 0.6 standard deviations is detectable with a one-sided t-test. With zero attrition, the mean detectable difference in covariates of interest drops to 0.5 standard deviations.

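### The pupil and eye-tracking regression on atomoxetine exposure has no within-child term, although each child is tested at up to four visits in a fixed order

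*Combined protocol and SAP*

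**What the plan says.** Section 4.1 sets out when pharmacodynamic data are taken: "Pharmacodynamic data will be obtained: baseline (Research Visit 1); when ATX is first initiated in a participant with the first dose (Research Visit 2"), then at steady state (Research Visit 3) and at the end of the study (Research Visit 4). The Schedule of Events row "Pupillometry during Posner's Cuing Task" is marked at all four visits. Within a session, "Measurements will be recorded for 162 trials which for both localization and discrimination tasks". A child who only partially completes the study must reach Research Visit 3 but not Research Visit 4 (Sections 8.2 and 20.1), so children contribute three or four sessions.

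In Section 20.1 (Pharmacodynamics), changes in Cmax and AUC0-∞ "will also be plotted against pupillometry and eye-tracking data gathered when testing participants with localization and discrimination tasks". To describe the relation, "the data will be regressed both linearly and non-linearly and best of fit statistics (Akaike Information Criteria and Bayesian Information Criteria) will be employed". The Pupillometry Analysis paragraph adds only that "Changes in performance during Posner Cuing Task will be measured as a function ATX exposure" and Cmax. The Cardiovascular Marker paragraph says the same of heart rate. None of these paragraphs names a random effect, a clustered variance, a visit term or the unit of analysis. The Pharmacodynamics paragraph does specify a nonlinear mixed-effects model, but only for the DHPG and metabolite parameters.

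**The concern.** Two measurements on one child are more alike than measurements on two children. A regression that treats child-visits as separate observations therefore gives a slope whose stated error is wrong. Its likelihood is wrong too, and AIC and BIC are computed from that likelihood. The authors provided for this with DHPG and were silent on the marker meant to show central transporter inhibition.

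There is a second problem. Every child goes through the visits in the same order: no drug, first dose, steady state, optimised dose. The trial has no control group. If children improve or habituate with repetition of the task, that change coincides with rising exposure and cannot be told apart from a drug effect.

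At stake are the shape and strength of the exposure-response relation for the central marker, and the plan's aim of separating central from peripheral drug action by setting pupil data beside heart rate.

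**Working it through.** The plan gives no power, standard error or sample size for this regression, so there is no figure of its own to reproduce.

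**Inputs from the documents.** 96 children (120 less 20% attrition, Section 20.2); three or four visits; zero exposure at Research Visit 1; Cmax,ss targets of 400, then 600 or 800 ng/mL (Section 5.1); α = 0.05 (Section 20.1).

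**Assumed, because the documents do not say.** The within-child correlation ρ of the pupil measure, the spread of exposure between children, the exposure level at the first dose, and the mix of final targets.

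**Step 1: limiting cases.** Let R be the true standard error of the pooled slope divided by the one that least squares reports, with m visits.
- Exposure constant within a child: R = √(1 + (m − 1)ρ). With m = 3 and ρ = 0.3, 0.5, 0.7, R = 1.26, 1.41, 1.55. At ρ = 0.5 the true two-sided error is 2(1 − Φ(1.96/1.41)) ≈ 17%.
- Exposure varying only within a child: R = √(1 − ρ) = 0.84, 0.71, 0.55. At ρ = 0.5 the true error is 2(1 − Φ(1.96/0.71)) ≈ 0.6%.

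So the sign of the error depends on where exposure varies. This design tries to shrink between-child differences and raises exposure within the child.

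**Step 2: exposures that follow the design.** Pooled least squares, 96 children, no true effect. Mean exposure is 0 at Visit 1, 250 at Visit 2 and 400 at Visit 3; at Visit 4 it is 400, 600 or 800 ng/mL with equal chance. Each child has a log-normal exposure factor (log-SD in the table) and each visit a further log-SD of 0.15. There were 3,000 replicates. Rejection at nominal 5%, for ρ = 0.4 / 0.6 / 0.8:

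| Between-child log-SD | Four visits | Visits 2–4 only |
|---|---|---|
| 0.1 | 2.0 / 0.8 / 0.3% | 2.7 / 1.8 / 1.3% |
| 0.2 | 3.1 / 1.9 / 0.5% | 3.9 / 4.3 / 3.5% |
| 0.4 | 4.8 / 4.5 / 3.9% | 7.7 / 8.8 / 9.4% |
| 0.6 | 6.8 / 7.7 / 8.9% | 9.3 / 10.9 / 13.7% |

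Taking change from Visit 1 as the outcome does not remove the problem. With a Visit 2 mean of 300, log-SD 0.3 and ρ from 0.3 to 0.7, R is about 1.11 to 1.12 and rejection 7% to 9%.

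**Step 3: practice.** Same set-up, no drug effect, with a drift of 0.1 SD per visit added (assumed).
- Pooled regression rejects in 30% to 50% of trials with four visits and 12% to 17% with Visits 2–4.
- A child random effect without a visit term (correlation taken as known) rejects in 53% to 99% and 16% to 71%. It is more exposed to drift because it relies more on within-child change.
- Child effect plus visit as a factor: 4% to 6% throughout.

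Repeated runs with slightly different settings put the pooled ranges at about 0.2% to 14% without drift and 13% to 48% with it. Those rounded ranges are used below.

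**Step 4: BIC.** The penalty per parameter is ln n. Counting children gives ln 96 = 4.56; counting child-visits gives ln(96 × 4) = ln 384 = 5.95. The plan does not say which n applies.

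**The case against.** The strongest reply is that the plan never says visits will be pooled. The sentence on regression would also fit a separate analysis at each visit, an analysis of one change per child, or a mixed regression. AUC0-∞ is listed as a parameter for the single dose, while the steady-state list gives AUC over the dosing interval, so read literally the AUC analysis might use one pair per child. This stands: pooling is an inference, and the point is conditional on it. The gap remains, because the plan collects repeated data and chooses none of these analyses.

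Four stronger readings are tempting and are not supported.
- **That the error is always understated.** A reader might simulate exposure that is exchangeable across visits (within-child correlation 0.3 to 1.0) and find 8% to 22% rejection with three visits, or 11% to 24% with four. Here exposure is zero for every child at Visit 1 and then titrated, so it is not exchangeable, and with good exposure control the pooled test is conservative.
- **That AIC/BIC will favour over-complex curves.** The likelihood is wrong, but BIC's penalty grows when visits are counted, so the net direction is not shown.
- **That the later paragraph confirms the method**, where "Linear and non-linear least squares regression analysis will be used to examine the correlation between DHPG fitted parameters and changes in eye-tracking" and pupillometry. That is a different analysis, by SLC6A2 group and plausibly with one value per child.
- **That the main hypotheses fall with this regression.** Hypotheses 1 and 2 concern genotype and clinical response, which have their own comparisons in Section 20.1.

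On practice, exposure need not rise in every child: Section 5.1 allows titration below 400 ng/mL, and Research Visit 3 has a wide window. That weakens the confounding but does not remove it, since every child still starts drug-free. No practice effect is documented; its size is assumed here.

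**Conclusion.** The concern holds in conditional form. The plan does not say how repeated visits enter the pupil and eye-tracking regression. If they are pooled, standard errors and AIC/BIC are invalid, and the direction depends on how well exposure is controlled between children. Under the assumed exposures and correlations a nominal 5% test runs at roughly 0.2% to 14%. Even where pooling is conservative, the fixed visit order leaves practice confounded with exposure: about 13% to 48% false rejection at an assumed 0.1 SD per visit. The exposure levels, their spread, ρ and the drift are all assumptions; the repeated visits, the fixed order, the missing control group and the absent within-child term come from the documents.

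Severity: should-fix. The regression serves the secondary objective on exposure, transporter inhibition and response, and the text presents it as descriptive.

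**What to change.** In Section 20.1 (Pharmacodynamics, Pupillometry Analysis and Cardiovascular Marker Analysis):

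1. State the unit of analysis: one summary per task and session, or trial-level data with a session level as well as a child level.
2. Fit the pupil, eye-tracking and heart-rate relations to exposure by linear or non-linear mixed models with a child random effect. Such a model can use children with three or four visits.
3. Compare linear and non-linear forms by maximum likelihood, AIC or BIC within that structure, and state the n used in BIC.
4. Report the exposure slope with and without visit number as a fixed factor, as a sensitivity analysis for practice. Say in advance that a slope which appears only without the visit factor cannot be attributed to the drug.

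The cost is SAP wording; SAS, R, NONMEM and Phoenix NLME are already listed. The real price is in item 4: the visit factor removes part of the exposure contrast that the design creates, so the interval widens. That is why both slopes should be shown rather than the adjusted one alone.

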#### *Global Neurotransmitter Analysis*

$k_{in, DHPG}$	Rate at which DHPG is created endogenously
$k_{out, DHPG}$	Rate at which DHPG is catabolized endogenously
$I_{max, DHPG}$	Maximal fractional inhibition produced by ATX
$IC_{50, DHPG}$	Concentration of ATX that results in 50% of maximal inhibition
$E_{max, DHPG}$	Maximum response through interaction of drug and drug target
$EC_{50, DHPG}$	Concentration of ATX that results in 50% of maximal response

Rates of formation and elimination ( $k_{in}$  and  $k_{out}$ ), maximal inhibition ( $I_{max}$ ), concentration at which 50% maximal inhibition is achieved ( $IC_{50}$ ), maximal response ( $E_{max}$ ), and concentration at which 50% maximal response is achieved ( $EC_{50}$ ) will be determined for all neurotransmitters assessed in the global neurotransmitter panel (see Appendix I for metabolite list). The Dietary Survey Questionnaire and microbiome information from saliva samples will be analyzed as possible covariates of the neurotransmitter profiles.

**Genetic Analysis:** Genome-wide analysis and single nucleotide polymorphism (SNP) analysis will be conducted on participant samples. Genetic testing (microarray SNP analysis, PCR sequencing, etc.) will be conducted to characterize variants in genes involved in disposition and response of ATX. Some examples of genes that may affect drug disposition and response include, but are not limited to, *CYP2D6*, *CYP2C19*, *ABCB1*, and *SLC6A2*. Genes associated with ADHD phenotype may also be analyzed, especially if ATX response (or lack thereof), is associated with a particular sub-population of individuals with ADHD. Additional testing may be conducted should more information become available regarding genes that may affect the prescribed drug's pharmacokinetic profile, pharmacodynamic characteristics, or clinical outcomes (i.e. safety, efficacy, or toxicity). Information on variants will be analyzed to determine impact on ATX safety, efficacy, or toxicity.

